1.2 SCHEMA

Example #1 Flow diagram (e.g., single arm, pre-posttest intervention)

1.3 SCHEDULE OF ACTIVITIES

2 INTRODUCTION

2.1 STUDY RATIONALE

Older adults are a growing population, with projections to reach 83.7 million by 2050. Furthermore, older adults are the most sedentary and least physically active adult population. It is estimated that nearly 90% of older adults 65 years of age or older do not meet the recommended levels of physical activity. Evidence suggests great health benefits can be achieved for older adults who are the most sedentary, and that replacing sitting with even light intensity walking can be beneficial.

2.2 BACKGROUND

Older adults (aged 60 and older) are a growing population, with projections to reach 83.7 million by 2050, almost double the population in 2012 (Ortman, Velkoff, & Hogan, 2014). Increasing age is associated with declines in many physiological systems (Sakuma & Yamaguchi, 20112) and increased risk for several non-communicable chronic health conditions (World Health Organization, 2009). Older adults often experience declines in balance, loss of muscle mass, reductions in muscle strength and endurance, and decreased cognitive function (Piercy et al., 2018; Sakuma & Yamaguchi, 2012; Salthouse, 2003; Warburton, Nicol, & Bredin, 2006) Collectively, these age-related declines can negatively impact older adult's physical function and quality of life (Taylor, 2014).

Physical activity is an important modifiable behavior demonstrated to reduce the risk for several age-related chronic diseases while improving physical function. (Piercy et al., 2018) Maintaining a physically active lifestyle is important for maintaining independence (Taylor, 2014), improving health-related quality of life (Choi, Lee, Lee, & Jung, 2017), and increasing performance in activities of daily (Dionigi, 2007; Piercy et al., 2018). Previous studies have demonstrated favorable financial impacts of physical activity-based wellness programs targeted to older adults.

Older adults are the most sedentary and least physically active adult population. Older adults spend an average of 9.4 hours per day engaged in sedentary behavior(Harvey, Chastin, & Skelton, 2014). The Physical Activity Guidelines for Americans recommend older adults to achieve a minimum of 150 minutes of moderate-to vigorous (MVPA), multicomponent physical activity per week which includes balance training, aerobic and muscle strengthening activities(Piercy et al., 2018). Moreover, older adult who cannot meet the guidelines are encouraged to do any amount of physical activity, to move more and sit less, in order to gain some health benefits(Piercy et al., 2018). However, it is estimated that nearly 90% of older adults 65 years of age or older do not meet the recommended levels of physical activity.(Shepherd, 2011) Evidence suggests great health benefits can be achieved for older adults who are the most

sedentary, and that replacing sitting with even light intensity walking can be beneficial. (Piercy et al., 2018)

Retirement communities and residential living facilities can be important settings to consider when delivering physical activity interventions to older adults. Evidence suggests that older adults living in these facilities may have an increased number of chronic diseases, are frailer, more inactive, and perform worse on physical function tests. (Kang, White, Hayes, & Snow, 2016; Mihalko & Wickley, 2003; Wert, Talkowski, Brach, & VanSwearingen, 2010) Retirement communities and residential living facilities can be an important setting to consider when delivering physical activity interventions to older adults.

Rosenberg et al. (2012) found that facility-dwelling older adults found a walking intervention to be feasible and effective for improving participants' daily steps, cognitive function. neighborhood barriers (i.e., hills, crime, traffic, unsafe crossing, or lack of places to walk) and satisfactions with walking opportunities (i.e., satisfaction with walking and exercise opportunities at their site, local area, and access to safe walking routes). However, a major limitation from this study was that participants used a pedometer to self-report their daily physical activity. With improvements in technology and the increasing use of wearable activity monitors, researchers can increase the quality of reliability of these study designs.

2.3 RISK/BENEFIT ASSESSMENT

2.3.1 KNOWN POTENTIAL RISKS

The physical risks include possible fatigue, and/or injury from participating in physical activity. There is a potential of loss of confidentiality of data. The intervention will promote engagement in low to moderate intensity physical activity which poses a low risk for injury.

2.3.2 KNOWN POTENTIAL BENEFITS

There is no guarantee of a direct benefit from participating in this study. However, participants may improve their health and might feel better.

2.3.3 ASSESSMENT OF POTENTIAL RISKS AND BENEFITS

We will screen participants carefully and exclude if they do not meet health related eligibility criteria. For the intervention risks, all participants will be informed about the potential risks of increasing their physical activity. However, the physical activity recommended will be of light-moderate intensity which the Physical Activity Guidelines for Americans recommend for all older adults. They will also be instructed to follow simple guidelines when doing physical activity. If something hurts, they should stop and only resume if it feels better. If they feel sick, they should seek medical attention. To minimize the risk of loss of confidentiality of data, we will take several steps including de-identifying and ID coding all electronic data, storing

electronic data on a password protected warehouse accessible only to the PI and the investigative team, and storing paper copies of data and informed consents under lock and key in the PI's office/laboratory

3 OBJECTIVES AND ENDPOINTS

OBJECTIVES	ENDPOINTS	JUSTIFICATION FOR ENDPOINTS	PUTATIVE MECHANISMS OF ACTION
Primary			
1. To determine the efficacy of MapTrek for improving physical activity levels of older adults living in a residential facility.	Assessments made at baseline, 8 weeks and 12 weeks.	We will determine whether the intervention was effective at 8 weeks and whether participants maintained outcomes at 12 weeks.	
Secondary			
1. To determine the efficacy of MapTrek for improving psychosocial outcomes(e.g., self-efficacy, social support, outcome expectations) among older adults living in a residential facility.		We will determine whether the intervention was effective at 8 weeks and whether participants maintained outcomes at 12 weeks.	
2. To determine the acceptability of MapTrek among older adults living in a residential facility.	We will assess acceptability at 8 weeks.	Participants will have just finished the intervention at 8 weeks.	
Tertiary/Exploratory			

4 STUDY DESIGN

4.1 OVERALL DESIGN

This intervention is a single arm, pre-post test pilot study.

4.2 SCIENTIFIC RATIONALE FOR STUDY DESIGN

Little physical activity research has been done within retirement communities, even though this is an optimal environment to deliver multilevel interventions (Jancey et al., 2017). Limitations with studies done in retirement communities include using a self-report measure of physical activity (Gallagher, Clarke, & Carr, 2016). Furthermore, studies were either not grounded in behavior change theory (Thompson, Kuhle, Koepp, McCrady-Spitzer, & Levine, 2014), or participants were not able to monitor their physical activity each day, receiving real-time feedback (Kerr et al., 2018). Similarly, there have been few mHealth physical activity interventions conducted with older adults. Of these studies, limitations include not clarifying if behavior change theory was used to drive the intervention design (Jonkman et al., 2018), and self-report measure of physical activity were used (Kim & Glanz, 2013; Muller, Khoo, & Morris, 2016). Finally, to our knowledge little research has been done on gamification of wearable activity monitors (Gremaud et al., 2018), specifically among older adults living in retirement communities.

Our team has developed a mHealth intervention called MapTrek (Gremaud et al., 2018). MapTrek is a mobile-phone based walking game, grounded in behavioral theory that places participants into virtual walking races for the purpose of encouraging more daily physical activity throughout the day. MapTrek was designed to be fun, engaging and interactive. In a recent trial, we found MapTrek to be feasible and efficacious at increasing physical activity among healthy sedentary office workers (Gremaud et al., 2018). Participants were randomized to a MapTrek intervention or a Fitbit control group. Participants in the MapTrek group took an average of 1,455 more steps/day than the control group. At the start of the intervention, MapTrek participants immediately increased their steps by 2,183 steps/day beyond the control group. After the intervention started, both groups started to decrease their average steps/day back to baseline values. The MapTrek group decayed significantly faster at 44.8 steps/day compared to the control group at 24.3 steps/day. Conversely, 70.9% of participants reported MapTrek increased their perceived level of support to be physically active, 77.7% felt motivated to be more active, 70.2% reported MapTrek was a fun, and 93.1% of participants reported MapTrek was easy to play (Gremaud et al., 2018). While these outcomes suggest MapTrek was effective for middle-aged adults in the community, we have not yet tested this approach among older adults. We believe MapTrek could be adapted for use and effective for increasing physical activity levels of older adults living in retirement communities. With the large and growing number of inactive older adults in the U.S., it is crucial that we identify effective and scalable approaches for promoting physical activity among older adults.

Translation of interventions to a population level has been slow and inconsistent. Significant effects on health can be made through widespread adoption and dissemination of interventions (Gonzales, Handley, Ackerman, & O'Sullivan P, 2012)

4.3 JUSTIFICATION FOR INTERVENTION

Older adults are a growing population, with projections to reach 83.7 million by 2050. Furthermore, older adults are the most sedentary and least physically active adult population. It is estimated that nearly 90% of older adults 65 years of age or older do not meet the recommended levels of physical activity. Evidence suggests great health benefits can be achieved for older adults who are the most sedentary, and that replacing sitting with even light intensity walking can be beneficial.

The overarching goal of our project is to develop an inexpensive and scalable tool to increase volume of physical activity in our target population, older adults living in a residential facility. MapTrek is a webbased application that allows participants to take a virtual walk in interesting locations around the world while tracking their progress against the progress of other older adults living in a retirement community. Steps are counted using a commercially available accelerometer (e.g., Fitbit), and participants see their progress overlaid on Google Maps. The overarching goal of our project is to develop an inexpensive and scalable tool to increase volume of physical activity in our target population, older adults living in a residential facility.

4.4 END-OF-STUDY DEFINITION

A participant is considered to have completed the study if he or she has completed the baseline assessment, the 8-week active intervention sessions, and the 4-week follow-up.

The end of the study is defined as completion of the 4-week follow-up assessment.

5 STUDY POPULATION

5.1 INCLUSION CRITERIA

Participants must have met the following inclusion criteria: 1) between the ages of 25 and 100; 2) do not have any physical or cognitive limitations that prevent them from walking comfortably; 3) have not participated in a study that uses MapTrek; 4) their doctor has not told them that is not safe to be physically active.

5.2 EXCLUSION CRITERIA

Exclusion criteria includes: 1) reporting any physical or cognitive limitations that prevent them from walking comfortably; 2) have participated in a MapTrek study before; 3) their doctor has told them it is not safe to be physically active; 4) there is any other reason why they shouldn't be physically active.

5.3 LIFESTYLE CONSIDERATIONS

N/A

5.4 SCREEN FAILURES

Screen failures are defined as individuals who meet one or more of the exclusion criteria. Individuals who meet one or more of the exclusion criteria will not be able to be re-screen for participation in the intervention.

5.5 STRATEGIES FOR RECRUITMENT AND RETENTION

We anticipate screening 110 individuals including women, minorities, and participants across the lifespan, in order to reach the target enrollment size of 100. We anticipate enrolling 100 participants, 50% female and 50% male. We anticipate accruing 75 older adults and 25 adults over 2-weeks.

At the Oaknoll off-site location, word about the study will be spread by word of mouth and advertisements. Advertisements will be displayed on TV monitors throughout Oaknoll. These materials will be distributed by the Activities Coordinator at Oaknoll. The research team members will spread information about the study through word of mouth. Interested participants will contact the Activities Coordinator to schedule a time and location for testing at Oaknoll. She will send out information about the study through Oaknoll's weekly news. If she receives any questions about the research beyond what is included in the brochures, ads, and posters, she will direct the person to contact a member of the research team. Once a participant shows interest in the study from seeing a poster advertisement or ad in the weekly news, she will schedule a time and location for testing at Oaknoll. The eligibly criteria will be listed in the ad, and all potential participants will be screened before the research team goes over the informed consent. Coercion and undue influence will be minimized by informing the subjects that participation in the study is completely voluntary and that they are free to quit the study at any time without penalty.

All participants will receive a Fitbit activity monitor. For compensation, all participants will be allowed to keep the Fitbit activity monitor at the end of the study. Participants who participate in the focus groups will receive a \$50 check for compensation.

6 STUDY INTERVENTION(S) OR EXPERIMENTAL MANIPULATION(S)

6.1 STUDY INTERVENTION(S) OR EXPERIMENTAL MANIPULATION(S) ADMINISTRATION

6.1.1 STUDY INTERVENTION OR EXPERIMENTAL MANIPULATION DESCRIPTION

We enrolled two different intervention groups, a group of older adults who live at Oaknoll and a group of Oaknoll employees. Enrolling a group of Oaknoll employees served two functions. First, it exposed the employees to MapTrek so that they can assist the residents with any technical problems or questions they may have during the course of the project period. Second, it fostered intergenerational engagement and generate excitement throughout the entire facility. Third, including employees was another avenue to increase social support for older adults, addressing the interpersonal level of the SEM. Physical activity interventions are likely to have greater effects when different levels are addressed at the same time.

At enrollment, each participant was provided with a Fitbit, shown how to wear it, and consented to the research team accessing their Fitbit data. Participants were asked to complete a baseline survey which asked about demographic information, their self-efficacy for exercise, social support for exercise, outcome expectations for exercise, and social isolation. Total participation in this project lasted for 14 weeks. The first two weeks were used to collected baseline data, where participants wore their Fitbit, but did not receive access to the MapTrek intervention. During the baseline period a kick-off event was held to answer participant's questions, and to give participants their team colored wrist bands. Participants were placed into one of three teams, and stayed on these teams for the duration of the intervention. Three teams were used to help foster competition in the event that one team was walking significantly more or less steps than the others.

After the two-week baseline period, participants received access to MapTrek and competed in four, two week-long races. Four two-week races were used so that teams had the opportunity to walk meaningful distances along each route (e.g., walking on the Grand Canyon Trail). The teams were assigned a new virtual walking route every two weeks. The team with the most steps at the end of two weeks were the winners.

We made environmental change to Oaknoll. Participants were encouraged to walk by large TV monitors placed in three common areas throughout the facility. A small Raspberry Pi computer will be connected to each monitor. The Raspberry Pi is a credit-card sized computer that plugs into a computer monitor or TV to be used as a normal desktop. Two other Raspberry Pi devices were placed at convenient locations throughout Oaknoll. As participants walked by, their Fitbit data synced to the Raspberry Pi. The Raspberry Pi was used to sync the Fitbit so that (a) participants did not have to manually sync their Fitbit and (b) participants who did not have a computer or smartphone could still participate. Every two weeks during the intervention a new walking route was revealed. The teams will be competing against each other, and their total number of steps will be used to move their character on the map. The map routes were Seattle to San Diego (1,936 miles), through Arizona, Colorado, and Utah (2,194 miles), from New York through Key West to Pensacola, FL (2,422 miles), and from Vancouver to Minnesota down the

Mississippi River to New Orleans (2,540 mils). We made sure each route was long enough in case every team member walked ~5 miles/day.

Three TV monitors were placed in public areas which displayed the virtual walking map, google maps view of the walking route, team leaderboard, and daily news. The daily news displayed messages each day that were developed based on Social Cognitive Theory (Appendix H). These behavior-change techniques addressed specific barriers to physical activity that older adults face such as health concerns, motivation and beliefs, low self-efficacy, access difficulties, and social support.

6.1.2 ADMINISTRATION AND/OR DOSING

The TV monitors displaying MapTrek will stay on during the entire 8-week intervention. The daily news will be updated once per day at 7:00AM CST.

6.2 FIDELITY

6.2.1 INTERVENTIONIST TRAINING AND TRACKING

Fidelity of the delivery of the intervention will include checking the TV monitors periodically to make sure they are displaying the MapTrek intervention.

6.3 MEASURES TO MINIMIZE BIAS: RANDOMIZATION AND BLINDING

N/A- this is a non-randomized intervention

6.4 STUDY INTERVENTION/EXPERIMENTAL MANIPULATION ADHERENCE

Intervention adherence will be monitored by participants syncing their Fitbit activity monitors.

6.5 CONCOMITANT THERAPY

6.5.1 RESCUE THERAPY

N/A

7 STUDY INTERVENTION/EXPERIMENTAL MANIPULATION DISCONTINUATION AND PARTICIPANT DISCONTINUATION/WITHDRAWAL

7.1 DISCONTINUATION OF STUDY INTERVENTION/EXPERIMENTAL MANIPULATION

When a subject discontinues from Residential MapTrek, the remaining study procedures will be completed as indicated by the study protocol. The data to be collected at the time of study intervention discontinuation will include the following:

• The reason(s) for discontinuing the participant from the intervention, and methods for determining the need to discontinue

7.2 PARTICIPANT DISCONTINUATION/WITHDRAWAL FROM THE STUDY

Participants are free to withdraw from participation in the study at any time upon request.

An investigator may discontinue a participant from the study for the following reasons:

- Significant study intervention non-compliance, unless varying compliance is an aspect of the study objectives
- Lost-to-follow up; unable to contact subject (see Section 7.3, Lost to Follow-Up)
- Any event or medical condition or situation occurs such that continued collection of follow-up study data
 would not be in the best interest of the participant or might require an additional treatment that would
 confound the interpretation of the study
- The participant meets an exclusion criterion (either newly developed or not previously recognized) that precludes further study participation

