8.3.3.3 EXPECTEDNESS

It is possible that participants could report musculoskeletal complications and/or cardiopulmonary complications that have been associated with vigorous bouts of physical activity. However, the intervention will not prescribe vigorous intensity activity, rather walking at a low to moderate intensity will be encouraged.

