9 STATISTICAL CONSIDERATIONS

9.1 STATISTICAL HYPOTHESES

- Primary Efficacy Endpoint(s): We hypothesize that participants will increase their average steps/day from
 baseline to the initial adoption of the active intervention, there will be a significant difference in average
 steps/day from baseline to the last week of the active intervention, there will be a significant difference in
 average steps/day from baseline to the follow-up phase post-active intervention, participants will
 experience a decrease in average steps/day each day from the start of the 8-week intervention to the
 end. two to week eight.
- Secondary Efficacy Endpoint(s): We hypothesize participants will increase their feelings of social support, self-efficacy, and outcome expectations, and decrease their feeling of social isolation from baseline to post-active intervention. We hypothesize this will be an acceptable multilevel mHealth intervention among older adults living in a retirement community.

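### Section 7.2 lets an investigator withdraw from the study a participant who newly develops an exclusion criterion; since the first is loss of comfortable walking, using it would tilt the step gain upward

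*Combined protocol and SAP*

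**What the plan says.** Section 7.2 opens its list of withdrawal grounds with "An investigator may discontinue a participant from the study for the following reasons". The verb is permissive and the scope is the study. The fourth ground is "The participant meets an exclusion criterion (either newly developed or not previously recognized) that precludes further study participation". It covers two groups: people who come to meet a criterion after enrolment, and people found late to have met one already.

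The first exclusion criterion in section 5.2 is "reporting any physical or cognitive limitations that prevent them from walking comfortably".

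The third ground in 7.2 begins "Any event or medical condition or situation occurs such that continued collection of follow-up study data" and has two limbs. One concerns the participant's best interest. The other concerns a possible need for further treatment that would confound the study's interpretation.

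Section 7.1 covers stopping the intervention: "When a subject discontinues from Residential MapTrek, the remaining study procedures will be completed as indicated by the study protocol".

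Section 9.1 sets the primary contrasts in average steps/day. One is the change in "steps/day from baseline to the last week of the active intervention"; another runs from baseline to the follow-up phase. Section 4.1 describes a single-arm pre-post pilot. Section 9.3, on analysis populations, has a heading and no text. Section 9.4.2 names a mixed model and repeated-measures ANOVA, with no missing-data rule and no sensitivity analysis.

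**The concern.** An entry criterion that is nearly a statement about the outcome can be applied again after enrolment. A resident who stops walking comfortably in, say, week 5 is likely to record fewer steps from then on. If the investigator uses the permission, that resident supplies no week-8 or week-12 steps, and the loss is tied to the values that go unrecorded.

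In a randomised trial a control arm would be exposed to the same rule. Here nothing shares the loss, so it passes straight into the estimated gain. The two contrasts would then describe residents who stayed able to walk comfortably, while the stated objective concerns older adults living in the facility. The 25% drop-out allowance in section 9.2 protects the number of participants; it does nothing about which participants are lost.

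**Working it through.** **The plan's own figure.** The documents give no figure for this bias. The nearest planning figure is the 42 participants in section 9.2. With a difference of 1,750, SD 2,000, 80% power and two-sided alpha 0.05 (sidedness assumed), the two-group normal approximation gives 2 × (1.960 + 0.842)² × 2,000² / 1,750² = 20.5, so 21 per group and 42 in all. The figure reproduces. Only the 1,750 is carried forward.

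**The chain in the text.**
1. Section 5.2: a limitation preventing comfortable walking is an exclusion criterion.
2. Section 7.2: a newly developed criterion that precludes further participation is a permitted ground for withdrawal from the study.
3. Section 9.1: the outcome is change in steps/day to the last active week and to follow-up.
4. Section 4.1: there is one arm.
5. Sections 9.3 and 9.4.2: no analysis set and no missing-data rule that would bring the withdrawn participants back.

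**Size, under assumptions.** Let *w* be the proportion withdrawn under this ground, *g* the gain in those who stay and *c* the change that those withdrawn would have shown.

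- Gain in all enrolled = (1 − *w*) × *g* + *w* × *c*
- Gain seen in those who stay = *g*
- Overstatement = *w* × (*g* − *c*)

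Take *g* = 1,750 from section 9.2. Both *w* and *c* are assumed; neither is in the documents.

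| *w* | *c* | Gain in all enrolled | Overstatement |
|---|---|---|---|
| 5% | 0 | 1,662.5 | 0.05 × 1,750 = 87.5 |
| 5% | -2,000 | 1,562.5 | 0.05 × 3,750 = 187.5 |
| 10% | 0 | 1,575 | 0.10 × 1,750 = 175 |
| 10% | -2,000 | 1,375 | 0.10 × 3,750 = 375 |

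**Does a mixed model repair it?** A random-intercept model with week as a factor was simulated 60 times per setting. Assumptions: 50 participants, baseline mean 5,000 (SD 1,700), within-person SD 1,000, onset of limitation between weeks 2 and 7, *g* = 1,750, *c* = -2,000, and 10% affected. Mean estimated week-8 gains (Monte Carlo standard error):

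- everyone followed: 1,372 (29)
- withdrawn at onset: 1,743 (23)
- one limited week recorded, then withdrawn: 1,720 (31)

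The first value agrees with the 1,375 in the table. The other two sit close to the gain of those who stay. A richer covariance structure might recover more in the third setting, where some low weeks are observed. No covariance structure can recover a fall that occurs only after recording stops.

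**The case against.** The strongest reply is that this is a qualified permission. The investigator may use it, and only where the criterion precludes further participation; a sore knee does not obviously preclude wearing a monitor. The wording looks generic, since section 7.3 still carries unfilled placeholders, and the study is a short pilot. All of this stands and makes the point a risk, not a certain loss. But discretion without criteria, in a single-arm study, is a reason to specify what happens to the data.

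Four stronger readings are tempting, and the documents do not support them:

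- *Anyone newly limited will be removed.* The permissive verb and the qualifier rule this out.
- *Sections 7.1 and 7.2 contradict each other.* They are separate routes, one out of the intervention and one out of the study. What is missing is a rule on which route a newly limited resident takes.
- *The fourth ground reaches only people who could safely go on wearing the monitor.* It also covers criteria that were met at entry but not recognised.
- *The intervention's own harms erase their data.* Section 8.3.3.3 does say "It is possible that participants could report musculoskeletal complications and/or cardiopulmonary complications", but it links these to vigorous activity and adds that vigorous activity will not be prescribed. Such complaints are one possible route to the criterion; the text does not present them as an expected effect of the game.

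It is also fair to say that the blank analysis population and the absent missing-data rule affect every kind of loss, including voluntary withdrawal and non-wear. That is why editing 7.2 alone would not be enough.

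**Conclusion.** The point holds as a design risk written into the rules: using the fourth ground for a newly limited resident removes low-step data selectively and biases both contrasts upward. The direction rests on two assumptions. The target is all enrolled residents, which the plan never states, and those withdrawn would have changed less than those who stay, which the nature of the criterion makes likely.

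The size is unknown. The ranges of 88 to 188 steps/day at 5% withdrawn and 175 to 375 at 10% are illustrations and should not be read as estimates. They scale directly with the proportion withdrawn and with the assumed fall, and they vanish if the permission is never used. The point merits an amendment because the change is small and the planned model would not correct the bias.

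**What to change.** 1. **Sections 7.1 and 7.2.** Reconcile them so that stopping the intervention is separate from stopping data collection. For a newly developed exclusion criterion, and for the confounding-treatment limb of the third ground, record the reason and, with the participant's agreement, continue Fitbit recording to week 12 and complete the exit survey. Without that second limb, a resident treated for a new walking problem could still be lost.
2. **Leave unchanged** the other grounds in 7.2, including non-compliance and the participant's best interest. The decision on continuing in the races stays as the protocol now assigns it.
3. **Section 9.3.** Define the step analysis set as all enrolled participants with baseline data, whatever happens later.
4. **Section 9.4.2.** Report withdrawals by reason. For data still lost, add a missing-not-at-random sensitivity analysis that sets the unrecorded changes below those of comparable participants who stay, over a stated range. The illustration above corresponds to shifts of 1,750 to 3,750 steps/day (1,750 − 0 and 1,750 + 2,000).

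**Cost.** A few sentences, and an estimated gain that may be smaller. Section 6.1.1 has data syncing as participants walk past devices, so residents who no longer pass them will need some help.

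**Timing.** The synopsis places the 8-week endpoint at 26 August 2019 and this version is dated 28 August 2019, so item 1 may come too late for the week-8 data. Items 3 and 4 can still be fixed before analysis.
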